passive EMS may reinforce its own use. Passive EMS should be safe and effective to use in most all patients on hemodialysis, with the exception of patients with pacemakers. Administration during the dialysis session addresses patient concerns regarding lack of time for exercise and access to suitable tools to exercise. It will also improve intradialytic clearance of phosphate and may stabilize intradialytic blood pressure that could have additional benefits in this population. Moreover, exercise training achieves the best results when it is supervised. Provision within the dialysis unit as part of the dialysis prescription provides the external motivation and social support of dialysis unit staff and other patients to help sustain this treatment. Finally, if passive EMS were shown to improve outcomes and lower annual cost per patient for in-center hemodialysis it would be readily adopted by dialysis providers and third-party payers.

C. Approach

1. Overview. We propose a clinical study to test the feasibility and efficacy of 16 weeks of passive exercise induced by electrical muscle stimulation (EMS) to improve markers of insulin resistance associated with morbidity and mortality in hemodialysis patients (Figure 1). EMS is provided sequentially for 15 minutes to both the right and left quadriceps muscle groups three times a week. The primary outcome measure will be improvement in insulin resistance measured using the homeostatic model assessment (HOMA-IR) and leptin-adiponectin ratio (LAR).

Figure 1.

The efficacy of the exercise training will be assessed by change in aerobic capacity measured by peak VO₂ and quadriceps muscle strength. Additional measures will include measurement of fat and

muscle content by dual energy X-ray absorptiometry (DXA) and anthropometry, measures of physical activity, nutritional status, depression, quality of life, anemia, mineral metabolism, dialysis blood pressure and serum levels of inflammatory cytokines and markers of oxidative stress.

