Following enrollment, baseline data and selected outcome markers will be assessed. Then all patients will undergo a 4-week care optimization phase during which time we will review the patient's dialysis care and make adjustments (if necessary) to meet standard of care guidelines as defined by CMS, KDOQI and KDIGO (Table 1). Outcome markers will be reassessed again after completion of the 4-week care optimization phase. At this time all patients will also undergo a baseline exercise test to measure peak VO₂ and a DXA scan for body composition analysis before starting EMS training.

| Table 1 | |
|---------------------------|--|
| Parameter | Optimized care goals |
| Vascular access | Discontinuation of central venous catheter and use of arteriovenous access |
| Fluid removal | Optimize dry weight. Limit UF rate to ≤ 13 ml/kg/hr |
| Solute removal | Minimum dialysis time ≥ 3.5 hours. Goal 4 hours. kT/V ≥ 1.4 |
| Acid-base | Pre-dialysis HCO ₃ between 22-27 mEq/L |
| Anemia | Hemoglobin 9.5-11 g/L, if on erythropoietin; Iron saturation $\geq 20\%$ |
| Ca, PO ₄ , PTH | Calcium, PO ₄ within normal levels; PTH ≤ 600 pg/ml |

EMS training will be done while the patient is on hemodialysis. At the first EMS training session, optimal EMS settings will be established and patients will be taught how to apply the electrodes and use the muscle stimulator. For patients who agree we will also do a muscle biopsy of the quadriceps (vastus lateralis) muscle at this first training visit before starting EMS training. Patients will be seen at the next dialysis session and again after 7 days to confirm that they are doing the EMS training properly. Patients are then seen at Day 14, 28, 42, 56, 84 and 112 after starting EMS training to assess for any adverse events, monitor progress with EMS training and adjust the EMS settings to make sure they are at the optimal tolerated intensity of muscle stimulation. The EMS training will continue for 16 weeks. At Day 56 and Day 112 (8 and 16 weeks) of EMS-training all the primary and secondary outcome variables including exercise stress test for peak VO₂ and DXA scan will be performed. For patients who agree we will also perform a muscle biopsy at a dialysis visit around Day 56 and Day 112 (not the same day as the exercise stress test). One month after stopping EMS training the patient will be seen and the outcome variables will be repeated except for the DXA scan and the exercise stress test.

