- Fasting blood sample (30 ml) for:
 - o Insulin and glucose
 - o Interleukin-6 (IL-6), tumor necrosis factor alpha (TNF α), C-reactive protein
 - o Glutathione (reduced and oxidized forms), glutathione peroxidase (GPx), superoxide dismutase (SOD), catalase (CAT), F2 isoprostane and protein thiols.
- Measure quadriceps muscle strength (bilaterally)
- 48 hour activity monitoring (using wrist watch monitor between dialysis sessions).
- DXA scan (performed in CRU)

- Perform exercise stress test to determine peak VO₂ (performed in CRU)

5.3 Visit 3. Initiate EMS training (Day 0). Performed in dialysis unit and CRU. 60-75 minutes. 30 minutes extra for optional muscle biopsy, if performed.

- Perform pre-EMS muscle biopsy before starting dialysis (optional)
- EMS training is done while on hemodialysis starting approximately 30 min after dialysis initiation.
 - o Record pre-EMS blood pressure and pulse
 - o Initiate EMS training on quadriceps muscle of leg not used for muscle biopsy for 15 minutes while on dialysis
 - o Measure and record BP and pulse before and just prior to completion of EMS training.
 - o Record any symptoms related to EMS
 - o Train patient how to use EMS device.

5.4 . Visits 4-8, 11. EMS training visits (Day 2/3 and 7). Performed in dialysis unit. Time required up to 45 minutes.

- Record any new medical conditions, symptoms or complaints
- Observe patient initiate and perform EMS training.
 - o Adjust stimulus intensity to maximum tolerated by patient for both legs
- Record EMS setting used.
- Record pre-dialysis sitting BP and pulse
- Record post-dialysis sitting BP and pulse

5.5 Visits 9 &12. Outcome assessment visits (Day 56 & 112 ± 7 days). Performed in dialysis unit or CRU where specified. Time required up to 4 hours.

- Record any new medical conditions, symptoms or complaints
- Record current dialysis orders
- Record episodes of dialysis hypotension (SBP<90 or symptoms needing saline, last 6 HD sessions)
- Record current exercise status (minutes of exercise per week)
- Record concomitant medications
- Malnutrition-inflammation (MIS) assessment
- Kidney Disease Quality of Life-36 (KDQOL-36) assessment
- Patient Health Questionnaire-9 (PHQ-9)
- Record vital sign measurements (predialysis or non-dialysis day, same timing as baseline measures)
- 6-minute walk test
- Record weight, waist circumference, hip circumference
- Record thigh circumference bilaterally
- Record most recent dialysis monthly lab tests.

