8. Statistical analysis/Power calculations.

This is a pilot feasibility and preliminary efficacy study to determine whether EMS can be delivered to this population and to assess the magnitude of the change and variability in the primary and secondary outcome measures. Data derived from this study will allow planning of a larger randomized controlled study. We plan to recruit up to 15 patients into the trial and complete the trial within 1 year. There will be 5 measurements of the primary and most of the secondary outcome variables in each patient. These will be performed at enrollment, after 4 weeks of "dialysis care

optimization" before starting the EMS intervention, then at 8 and 16 weeks after initiation of the EMS intervention and finally 4 weeks after stopping EMS. The DXA scan, measurement of peak VO₂ will only be performed three times (before starting EMS and then again at 8 and 16 weeks of EMS training). The optional muscle biopsy for gene expression analysis will be performed up to 4 times in patients who agree to this analysis (before and after the first EMS treatment, at 8 and 16 weeks of EMS training). Summary statistics will be used to describe and analyze the data. Changes over time in the outcome variables will be analyzed using the Friedman analysis of variance by ranks to determine if there was a statistically significant effect of EMS. A P<0.05 will be considered statistically significant. Regression analysis will be used to determine if the change in HOMA-IR or LAR is correlated with the magnitude of the observed exercise training effect (i.e. the increase in peak VO₂ or quadriceps muscle strength at 4 months) or maximum intensity of EMS stimulation used during training.

Based on an estimated baseline mean (\pm SD) HOMA-IR score of 4.8 (\pm 1.7) mg/dl· μ U/ml, a sample size of 15 patients will provide 80% power to detect a 28% decrease in the HOMA-IR score (by a paired t-test analysis) at the P=0.05 level. This decrease in HOMA-IR score would be predicted to be associated with a clinically significant reduction in mortality.³³

9. Selected methods

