9.1. HOMA-IR and leptin-adiponectin ratio (LAR). HOMA-IR and LAR are both separate measures of insulin resistance. Patients will fast for 12 hours and withhold taking their morning insulin or oral antidiabetic agents prior to the test. Venous blood (10 ml) will be drawn into a red top tube (serum separator) placed on ice and centrifuged at 3,000 rpm at 4°C to separate serum. The serum is aliquoted and stored at -80°C until assay. Fasting serum insulin (μ U/ml) is measured using an electrochemiluminescent assay and fasting serum glucose (mg/dl) by a hexokinase assay in the UIHC clinical chemistry lab. HOMA-IR score is calculated using the homeostatic model assessment equation (HOMA-IR = fasting glucose (mg/dl) x fasting Insulin (μ U/mL) / 405). Serum leptin (ng/ml) and adiponectin (ng/ml) are measured by RIA using Linco kits (Linco, St. Charles, MO) in [name] lab at Iowa.

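### A significant change over time is to be read as an effect of EMS, although there is no concurrent control and recorded changes in background treatment enter no HOMA-IR or LAR analysis

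*Combined protocol and SAP*

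**What the plan says.** Section C.1 presents the study as a test of the "feasibility and efficacy of 16 weeks of passive exercise induced by electrical muscle stimulation (EMS) to improve markers of insulin resistance". Section 4.1 defines the primary outcome as the change in HOMA-IR or LAR after 8 and 16 weeks of EMS. Section 8 plans up to 15 patients, measured five times. It applies the Friedman test to changes over time "to determine if there was a statistically significant effect of EMS" and adds: "A P<0.05 will be considered statistically significant". There is no control group. Section 8 describes a pilot of feasibility and preliminary efficacy and states: "Data derived from this study will allow planning of a larger randomized controlled study".

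On background treatment:

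- In the four weeks before EMS (Section C.1), staff review care and "make adjustments (if necessary) to meet standard of care guidelines". Table 1 lists the goals and has no glycemic item.
- Section 3.1 does not exclude diabetes. Section 9.1 has patients "withhold taking their morning insulin or oral antidiabetic agents prior to the test", so patients on these drugs are expected.
- The visit lists in Sections 5.1, 5.2, 5.5 and 5.7 include "Record concomitant medications" and the current dialysis orders.
- No section requires either to be stable after Day 0, and no analysis of HOMA-IR or LAR refers to these records.

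**The concern.** With no concurrent control, the reference for the primary outcome is the patient's own value before EMS. A change from that value reflects EMS only if nothing else that moves HOMA-IR changed over the same weeks. Section 9.1 computes HOMA-IR as fasting glucose times fasting insulin divided by 405, so a change in a glucose-lowering drug acts on its inputs directly. A drug started or increased can look like benefit from EMS, and one reduced can hide it. Section 8 would attribute either result to EMS.

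What is at stake is the conclusion and its later use. The estimated change is meant to inform a randomized trial, and a change produced partly by background treatment could lead to the wrong size for that trial.

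**Working it through.** **1. The plan's own figure.** Inputs from Section 8: HOMA-IR mean 4.8, SD 1.7, n = 15, 28% decrease, paired t-test, P = 0.05. Target change = 0.28 × 4.8 = 1.344. Taking 1.7 as the SD of the paired difference and a two-sided test, the noncentrality is 1.344 / 1.7 × √15 = 3.06. With 14 degrees of freedom the power is 81.2%, which agrees with the stated 80%. SD of difference = 1.7 × √(2(1 − ρ)), so the match implies a within-patient correlation ρ of 0.5. The present point does not affect this calculation.

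**2. What a background change does to the mean.** The documents do not say how many patients change treatment or by how much, so these inputs are assumptions. If k of 15 patients have a change that lowers HOMA-IR by a fraction d, the mean falls by (k/15) × d × 4.8.

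- k = 3, d = 0.28: 0.27, or 0.27 / 1.344 = 20% of the target change.
- k = 5, d = 0.50: 0.80, or 0.80 / 1.344 = 60% of the target change.

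**3. What it does to the planned test.** Simulated trials with no EMS effect: n = 15, normal data, mean 4.8, SD 1.7, ρ = 0.5. The background change is present from week 8 onward. The Friedman test uses the pre-EMS, week 8 and week 16 values.

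| Patients with a change, all downward | P<0.05, 28% fall | P<0.05, 50% fall |
|---|---|---|
| 0 | about 5% | about 5% |
| 3 | 5.7% | 7.7% |
| 4 | 7.6% | 11.2% |
| 5 | 9.6% | 16.2% |

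If each change is equally likely to be up or down, the rate for 3 to 5 changers stays at 4.4-4.7%. With one or two changers, all downward, it is 4.7-5.5%.

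**4. Whether another part of the plan closes the gap.**

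- *Care optimization (C.1, Table 1):* comes before EMS, has no glycemic item and does not fix later care.
- *Stratification by care goals (4.1):* uses status at one time point, not later changes.
- *Regression of HOMA-IR or LAR change (Section 8):* its explanatory variables are peak VO₂, quadriceps strength and stimulation intensity. Treatment changes are not among them.
- *Measurement four weeks after EMS:* still within-patient, and a lasting drug change carries into it. Section 4.2.11 names the post-EMS phase as a comparator for blood pressure and pulse. No such contrast is set out for HOMA-IR or LAR.

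**The case against.** The strongest reply is that this is a pilot of at most 15 patients that says it is preparing a randomized trial and measuring magnitude and variability. Much of the proposed rewording is therefore already its stated aim. The four safeguards in the working show that attribution was considered, and the protocol itself prompts no change in glucose-lowering drugs. All this is fair and limits the weight of the point. It does not remove the sentence in Section 8 that turns a time effect into an effect of EMS.

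A reader might infer more than the documents support:

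- *That the false-positive rate is badly inflated.* This needs several changes in one direction, which nothing in the documents predicts. With three changers the rate is close to nominal.
- *That a general drift in all patients is the same problem.* It is separate: a list of drug changes would not reveal it. Only a concurrent control would.
- *That a change of vascular access distorts IL-6 or CRP.* The documents do not state this link, so it forms no part of the point.
- *That no recorded treatment data are used at all.* Erythropoietin, iron and phosphate-binder doses are plotted (4.2.9, 4.2.10), and care status at one point is a stratifier. The gap concerns changes in glucose-lowering drugs and dialysis orders in the HOMA-IR and LAR analyses.

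**Conclusion.** The point holds in this form: a significant Friedman result would show that HOMA-IR or LAR changed over time, and the design cannot say that EMS caused it. This follows from the single arm alone and needs no assumption. The unused treatment records add one concrete and avoidable route to a wrong attribution.

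The numerical size is modest and conditional. It is about 6-8%, 8-11% and 10-16% for 3, 4 and 5 one-direction changers with falls of 28-50%, against about 5% with none, and there is no inflation when directions balance. These figures assume normal data, a within-patient correlation of 0.5 and a three-visit test. Section 8 does not say which of the five visits enter the test. Because the study is a pilot, the remedy is wording and a descriptive display, not a new design.

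**What to change.** In Section 8:

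1. Replace the stated purpose of the Friedman test with *to estimate the change during the EMS period*. Report the change in HOMA-IR and LAR with its interval, and state that attribution to EMS is left to the planned randomized study.
2. From the records already collected, flag and list each patient's changes from Visit 2 in glucose-lowering drug or dose. Show HOMA-IR and LAR with and without values taken after such a change, as a supportive descriptive analysis. The visit lists do not say that dose is captured, so the data form should make this explicit. Medications are recorded at Visits 9 and 12 but blood is drawn at Visits 10 and 13, so changes should be dated.

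The cost is protocol wording and one extra display, with no new visits or patients. There are two drawbacks. The restricted display has fewer patients: by the paired t-test calculation above, power for the 28% change is about 78%, 74% and 70% with 14, 13 and 12 patients. Leaving out values after a drug change also conditions on something that happens after EMS starts and that EMS may itself cause. If EMS improved glycemia and drugs were then reduced, the rule would remove responders. The display should therefore not serve as a decision rule.

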Exclusion criteria include: presence of a cardiac pacemaker or presence of any other implanted electrical stimulation device, uncontrolled hypertension (SBP>170 mmHg), unstable angina, heart attack within the last month, expected survival <6 months, unsuitable for participation based on physician assessment, unwilling or unable to give informed consent.

4. Outcome measures.

4.1 Primary Outcome.

The primary outcome measure will be the change in insulin resistance as determined by either HOMA-IR or LAR after 8 and 16 weeks of EMS training. The analysis will also be stratified by whether patients achieved optimum dialysis care goals at randomization to see if optimization of care influenced the response to EMS. The correlation between change in HOMA-IR or LAR with change in aerobic capacity (peak VO₂) and quadriceps strength after 16 weeks training and with maximal EMS training intensity (in mV) achieved will be assessed to determine if change in insulin resistance depends on intensity of training.

4.2. Secondary outcomes measures.

4.2.1. Aerobic capacity and quadriceps strength. The effect of EMS on quadriceps muscle strength will be assessed 5 times (Visits 1, 2, 9, 12 and 14 in Figure 1) : at baseline, pre-EMS training, at 8 and 16 weeks of EMS training and again 4 weeks after stopping EMS training. Quadriceps muscle strength will be determined using a belt-stabilized portable dynamometer.⁴³ Change in peak VO₂ will be measured 3 times (Visits 2, 9 & 12): pre-EMS training and after 8 and 16 weeks of EMS training. Peak VO₂ will be determined using graded exercise treadmill test using a Balke protocol. Cycle ergometry will be used to determine peak VO₂ in patients who can't walk on a treadmill but can do cycling. This will determine if EMS produced an increase in quadriceps strength or improvement in aerobic capacity after 8 and 16 weeks of training. It will also determine how rapidly the effect on muscle strength is lost after stopping EMS training.

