treatment and after 8 and 16 weeks of EMS training to determine the chronic effect of EMS training on muscle gene expression. Gene expression analysis will be done using Affymetrix Human Exon 1.0 ST arrays as previously described.⁷⁰ We will first examine specific genes that are highly overexpressed or under-expressed after acute and chronic exercise compared to the baseline (pre-EMS). We will also look for biological pathways activated or suppressed by acute and chronic exercise specifically looking at pathways relating to muscle glucose metabolism and insulin response, mitochondrial biogenesis and function, muscle phenotype, growth and energy metabolism, oxidant stress and inflammation. A future goal of this research is to compare the gene expression response to EMS in this study with that seen in patients with normal renal function and varying levels of CKD to see if the gene response profile is qualitatively different in patients with varying levels of kidney function. We are also interested how the gene expression profiles seen with EMS compare to that seen with traditional volitional aerobic exercise to determine if EMS activates different genes or biological pathways than volitional exercise.

5. Visits & Assessments.

Patients will be identified from the population of patients on regular maintenance hemodialysis at one of the University of Iowa dialysis units. Potential subjects will be approached at a dialysis visit and informed of the study.

5.1. Visit 1. If they indicate an interest in participating we will proceed with obtaining written informed consent and confirm that they meet all the inclusion criteria and none of the exclusion criteria.

- Obtain informed consent to participate and consent to access additional appropriate medical records
- Review inclusion and exclusion criteria

Baseline data collection (Day -35 to -28). Performed at dialysis unit or CRU as appropriate. Up to 4 hours time.

- Record demographics and baseline disease characteristics
- Record past medical history and current review of symptoms
- Record current dialysis orders
- Record episodes of dialysis hypotension (SBP<90 or symptoms needing saline, last 6 HD sessions)
- Record baseline exercise status (minutes of exercise per week)
- Record concomitant medications
- Malnutrition-inflammation (MIS) assessment
- Kidney Disease Quality of Life-36 (KDQOL-36) assessment
- Patient Health Questionnaire-9 (PHQ-9)
- Record sitting blood pressure and pulse

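### Does the 80% power figure mislead because it is for a paired t-test while EMS is to be judged by a five-visit Friedman test?

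*Combined protocol and SAP*

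**What the plan says.** Everything that bears on power is in section 8 (Statistical analysis/Power calculations).

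- Recruitment: "We plan to recruit up to 15 patients into the trial".
- Measurements: "There will be 5 measurements of the primary and most of the secondary outcome variables in each patient". They fall at enrollment, after the 4-week care optimization, at 8 and 16 weeks of EMS, and 4 weeks after EMS stops.
- Test for an effect of EMS: "Changes over time in the outcome variables will be analyzed using the Friedman analysis of variance by ranks", with significance at P<0.05.
- Power: the sentence opens "Based on an estimated baseline mean" (4.8, SD 1.7) and continues that "a sample size of 15 patients will provide 80% power to detect a 28% decrease in the HOMA-IR score (by a paired t-test analysis". The significance level used there is 0.05.

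Section 4.1 defines the primary outcome as the "change in insulin resistance as determined by either HOMA-IR or LAR after 8 and 16 weeks of EMS training". Section 5 places two fasting samples before EMS: one under "Baseline data collection (Day -35 to -28" in 5.1, and one at the pre-EMS visit (Day -7 to 0) in 5.2. The only analysis that the plan assigns to paired t-tests is that of mRNA levels, in section 9.8.

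**The concern.** Section 8 names one test for the power and another for the analysis. The 80% is also the only quantitative support for 15 patients, and several of its inputs have to be inferred.

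- The 1.7 is labelled a baseline SD, but a paired t-test needs the SD of within-patient change.
- Sidedness is not stated.
- Fifteen is both the recruitment ceiling and the number of pairs in the calculation, so there is no margin for a lost patient. The standard Friedman test also needs complete visits from each patient.
- The pair is not named. Two pre-EMS samples and two during EMS give 2 × 2 = 4 candidates. The two that start at enrollment would include any effect of care optimization.

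If the Friedman test had clearly less power than 80%, a non-significant result could be read as stronger evidence against EMS than it is.

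**Working it through.** **Inputs from section 8.** Mean 4.8, SD 1.7, decrease 28%, alpha 0.05, n = 15. **Assumed, because not given:** a two-sided test, the SD of change, the within-patient correlation, the time course, and the number evaluable.

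**1. Reproducing the plan's figure.**

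- Difference: 0.28 × 4.8 = 1.344 HOMA-IR units.
- Standardized difference, with 1.7 as the SD of change: 1.344 / 1.7 = 0.791.
- Noncentrality: 0.791 × √15 = 3.06, on 14 degrees of freedom.
- Two-sided power from the noncentral t distribution: 81.2%.
- One-sided power would be 89.7%, and the two-sided normal approximation gives 86.5%.

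The stated 80% is therefore a two-sided paired t-test with 1.7 as the SD of change. Exactly 80% corresponds to an SD of change of 1.73. The smallest n that reaches 80% at 1.7 is 15.

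**2. What an SD of change of 1.7 implies.** With equal SDs at both visits, SD of change = 1.7 × √(2(1 − ρ)), which equals 1.7 when ρ = 0.5. If the SD falls in proportion to the mean, the later SD is 0.72 × 1.7 = 1.224. Then √(1.7² + 1.224² − 2ρ × 1.7 × 1.224) equals 1.7 when ρ = 0.36. Neither is extreme, and the documents do not settle either.

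**3. Sensitivity of the paired t-test.**

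| SD of change (assumed) | Evaluable n | Power |
|---|---|---|
| 1.7 | 15 | 81% |
| 1.7 | 14 | 78% |
| 1.7 | 13 | 74% |
| 1.7 | 12 | 70% |
| 2.0 | 15 | 68% |
| 1.3 | 15 | 96% |

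The SD of change can push power either way. Loss of patients can only lower it.

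**4. Power of the Friedman test, simulated.** Normal data, five complete visits, chi-square critical value on 4 degrees of freedom, SD 1.7 at every visit and correlation 0.5, so that the SD of change is again 1.7. There were 40,000 runs per cell, and simulated type I error was 0.044 (n = 15) and 0.046 (n = 12). The profile gives the fraction of the 1.344 decrease present at enrollment, pre-EMS, week 8, week 16 and post-EMS.

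| Profile | n = 15 | n = 12 |
|---|---|---|
| 0, 0, 0, 1, 0 | 74% | 61% |
| 0, 0, ½, 1, ½ | 69% | 56% |
| 0, 0, ½, 1, 0 | 75% | 63% |
| 0, 0, 1, 1, 0 | 92% | 83% |
| 0, 0, 1, 1, 1 | 92% | 83% |
| 0, 0, 1, 1, ½ | 85% | 74% |
| 0, 0, ½, 1, 1 | 85% | 74% |

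With 15 patients, four of the seven profiles exceed the paired t-test's 81%. With 12 patients, the same four exceed its 70%.

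**5. Does a shrinking SD alter this?** If the SD falls with the mean and the correlation is matched at 0.36, so that the SD of change at full effect stays 1.7, Friedman power is again about 69–92% (n = 15) and 56–84% (n = 12). If the correlation is instead held at 0.5, Friedman power rises, but the SD of change is then 1.52 and the paired t-test itself has 89%. That rise comes from a smaller SD, not from the choice of test.

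**The case for a change.** The best case for a change is this. Section 8 also calls the study one of preliminary efficacy, sets a significance threshold and intends the data to plan a larger randomized trial. The number that supports 15 patients ought therefore to belong to the test that will be reported. Complete data from all 15 is optimistic: section A cites mortality of 20% per year and 1.9 admissions per patient per year, against about 6 months of participation. Naming the pre-EMS visit and week 16 would isolate the training period and fit the planned regression on the increase in peak VO₂ or "quadriceps muscle strength at 4 months".

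Part of this stands. The SD of change, the pair and the evaluable number are not stated, and 15 leaves no reserve. Section 3.1 limits attrition, by requiring an expected stay of at least 6 months in a participating unit and excluding expected survival under 6 months, but does not remove it. One lost patient costs about 3 points.

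The rest does not carry. The power sentence itself says that it refers to a paired t-test, so a careful reader is not told that it is Friedman power. Sizing on a simple paired contrast and testing with a rank method is an approximation, and here it has no consistent direction. The same difference and SD would enter the calculation for any of the four pairs, so naming one would leave the 80% as it is. An outcome defined as change after 8 and 16 weeks of EMS already points to the pre-EMS visit as reference, although the protocol uses the word baseline loosely. Making week 16 by paired t-test the main analysis would set aside week 8, which section 4.1 also names, and would demote the only test planned for the effect of EMS. That is a preference with its own costs.

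**Conclusion.** The concern is accurate as an observation on reporting but calls for no change. The 80% is correct for the test it names: 81.2%, if the SD of change is about 1.7 and all 15 patients are evaluable, and 70% if only 12 are. It is not the power of the planned Friedman test, which is about 69–92% with 15 patients and 56–84% with 12. Those ranges rest on assumed normal data, an SD of change of 1.7, complete visits and seven assumed time courses.

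The missing inputs can be recovered from the figure itself. The SD of change is also among the things this pilot sets out to learn, since section 8 gives its purpose as assessing the size and variability of change. Adding the assumptions would document the calculation without altering the sample size, the visits, the analysis or any conclusion. When the results are written up, a non-significant Friedman test should not be set against the 80%; the observed change with its confidence interval is the more useful result to carry forward.

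### HOMA-IR is calculated from measured serum insulin, insulin-treated patients are pooled with all others, and no analysis shows whether a change in injected insulin explains the result

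*Combined protocol and SAP*

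**What the plan says.** Section 4.1 makes the primary outcome the "change in insulin resistance as determined by either HOMA-IR or LAR after 8 and 16 weeks of EMS training". The power statement in section 8 uses HOMA-IR alone.

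Section 9.1 gives the score as "HOMA-IR = fasting glucose (mg/dl) x fasting Insulin" divided by 405. Serum insulin is "measured using an electrochemiluminescent assay"; nothing is said about detection of injected insulin or its analogues, and C-peptide is not measured. On preparation, section 9.1 requires a 12-hour fast and asks patients to "withhold taking their morning insulin or oral antidiabetic agents prior to the test". Evening insulin, long-acting insulin and time since the last injection are not mentioned.

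Section 3.1 does not remove insulin users. Its list opens "Exclusion criteria include: presence of a cardiac pacemaker or presence of any other implanted electrical stimulation device, uncontrolled hypertension" and names neither diabetes nor insulin treatment anywhere. Section 6.2.6 also anticipates diabetic patients.

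Section 8 analyses changes over time with the Friedman test in up to 15 patients, in one arm. It has no exclusion, stratification, adjustment or sensitivity analysis by insulin use. The only stratification, in section 4.1, is by dialysis-care goals, and Table 1 contains none on glucose-lowering treatment.

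**The concern.** HOMA-IR is meant to reflect the insulin the patient's own pancreas secretes against a given glucose. In an insulin-treated patient the measured insulin may include an injected part. If that part differs between visits, because the dose, the product or the interval since the last injection changed, the score changes in proportion. Each patient is in the study for about 6 months, so changes of regimen are plausible.

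In a before-after study there is no parallel group in which such changes would also appear. They can therefore hide an EMS effect or look like one. Section 8 says the study is to estimate the size and variability of change for a later randomized trial, so a distorted mean or SD would carry into that design. The planned regression of HOMA-IR change on training effect has the same weakness.

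**Working it through.** **Inputs from the documents.** Baseline HOMA-IR 4.8, SD 1.7, n = 15, a 28% fall, paired t-test, P = 0.05 (section 8). HOMA-IR = glucose × insulin / 405 (section 9.1).

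**1. The plan's own figure.** Planned fall = 0.28 × 4.8 = 1.344. Standardised effect = 1.344 / 1.7 = 0.791. Exact two-sided paired-t power at n = 15 is 81.2%, so the stated 80% reproduces. This takes 1.7 as the SD of the change, which implies a within-patient correlation of 0.5 if the visit SDs are equal.

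**2. Sensitivity of the score to measured insulin.** At fixed glucose, 1 µU/ml of insulin moves HOMA-IR by glucose / 405. The insulin change equal to the whole planned fall is 1.344 × 405 / glucose. The glucose values are assumptions.

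| Glucose (mg/dl) | HOMA-IR per 1 µU/ml | Insulin at HOMA-IR 4.8 (µU/ml) | Insulin change equal to 1.344 (µU/ml) |
|---|---|---|---|
| 100 | 0.25 | 19.4 | 5.4 |
| 150 | 0.37 | 13.0 | 3.6 |
| 200 | 0.49 | 9.7 | 2.7 |

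**3. Shift in the group mean (illustration).** Assume glucose 150 mg/dl and a mean change of 5 µU/ml among users. Group shift = share of users × 5 × 150 / 405.
- 20% users: 0.37, or 28% of 1.344.
- 50% users: 0.93, or 69% of 1.344.

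**4. Noise, paired t-test (illustration).** Assume 5 of 15 are users and their SD of change is m × 1.7. Overall SD = 1.7 × √((10 + 5m²) / 15).
- m = 1.5: SD 2.02, power 67%.
- m = 2: SD 2.40, power 52%.
- Users removed, n = 10, SD 1.7: power 61%, detectable fall about 35%.

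**5. The same scenario under the planned Friedman test (simulation).** Assumptions: independent normal errors with visit SD 1.7 / √2, so that a difference between two visits has SD 1.7; a fall of 1.344 at week 16 and half of it at week 8; in the five-visit version, also half at follow-up. Section 8 does not say which visits enter the test, so both versions are shown.

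| Patients analysed | Three visits | Five visits |
|---|---|---|
| 15, no extra noise | 58% | 69% |
| 15, 5 users at 1.5 × SD | 48% | 56% |
| 15, 5 users at 2 × SD | 42% | 50% |
| 10 non-users only | 40% | 46% |

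The paired-t figures in step 4 are therefore not the power of the planned test. Under the planned test, dropping the users costs slightly more power than keeping them, even at doubled SD. Steps 4 and 5 cover noise only, not a directional shift.

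**6. Are the data for a second analysis collected?** Concomitant medications are recorded at Visits 1, 2, 9, 12 and 14. Fasting blood is drawn at Visits 1, 2, 10, 13 and 14. At weeks 8 and 16, drugs and blood thus belong to different visits. The fasting-sample lists in sections 5.1, 5.2, 5.6 and 5.7 name insulin and glucose, but not leptin or adiponectin.

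**The case against.** Several objections have force.

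- **Silence is not permission.** A reader might infer that patients hold only the morning dose and continue all other insulin. Section 9.1 does not say so; it does not address other doses. How much injected insulin is counted depends on regimen, timing and assay specificity, none of which is given. The text supports that injected insulin can enter the score, not that it does. The 12-hour fast and the withheld morning dose already limit part of the problem.
- **Patients are their own controls.** A steady injected level at steady glucose produces no within-patient change. Bias needs a change between visits, and nothing in the documents indicates its direction.
- **Ranks limit outliers.** The Friedman test ranks within patient, so a few extreme scores count for less than in a t-test. A wrong ordering of visits within an insulin user still counts.
- **LAR is already a primary measure** and has no insulin term. That helps only if leptin and adiponectin are actually sampled, and the visit lists omit them.
- **A pilot should show variability.** Restricting the primary HOMA-IR analysis to non-users would hide variability that the study is meant to measure, and would lose power.

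The last objection is a good reason not to restrict the primary analysis. None of them supplies a rule for telling a change in injected insulin from an EMS effect.

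**Conclusion.** The concern holds as a gap in the analysis plan. Insulin users are eligible, their measured insulin goes directly into a primary measure, and the plan as written yields a single pooled HOMA-IR result with no means of checking it. For an individual patient the sensitivity is large: a few µU/ml equals the entire planned effect, at the glucose values assumed.

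Two stronger readings are not supported. One is that the 80% power claim is wrong: it reproduces on its own inputs, and the losses shown rest on an assumed number of users and assumed variability. The other is that HOMA-IR is demonstrably biased here: bias requires a change in injected insulin between visits that the assay detects, and the documents establish neither. This is a worthwhile and inexpensive improvement, not a flaw that invalidates the study.

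**What to change.** 1. Keep the all-patient HOMA-IR analysis. In section 8, prespecify a second HOMA-IR analysis that leaves out patients on exogenous insulin and patients whose glucose-lowering regimen changed between Visit 2 and week 16.
2. Report HOMA-IR change and its SD separately for users and non-users. State that a HOMA-IR change will not be attributed to EMS unless it is also seen without the excluded patients.
3. Report LAR for all patients, and add leptin and adiponectin to the fasting-sample lists in sections 5.1, 5.2, 5.6 and 5.7.
4. Record insulin type, dose and time of last injection with each fasting sample, in particular at Visits 10 and 13. State whether the assay detects injected insulin.

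This records treatment and does not alter it. The cost is some SAP wording, a few data fields, two assays added to the visit lists and one extra analysis. That analysis will be imprecise: with 10 non-users, paired-t power for a 28% fall is about 61%, and lower in the Friedman simulations above. It should be read for consistency of direction and size, not for significance.
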